Development and Evaluation of a New Infant Nutrition Screening Tool (Infant Yorkhill Malnutrition Score)

Introduction

A large number of children experience undernutrition related to or resulting from their illness. Hospitalized children are at a high risk of developing malnutrition particularly children with underlying disease and clinical conditions (Joosten KF and Hulst JM, 2008, 2010). In addition malnutrition has been associated with an increase in length of hospital stay and consequently the cost of providing health care (Campanozzi A et al, 2009). Therefore, the identification of children at risk of undernutrition is an important part of any programme for providing optimal health and treating of hospitalized patients. Quality Improvement Scotland has recently published standards for Food Fluid and Nutritional Care, which state that all patients should be screened for undernutrition on admission and periodically during their stay at hospital (NHS QIS 2003).

Common methods of assessing nutritional status in children include a combination of dietary, anthropometric, biochemical measures and clinical signs. It is not possible for all admitted patients to have a complete nutritional assessment, but nutritional screening aims to identify those who are malnourished or at risk of becoming so to allow them to be assessed in more detail. In terms of anthropometric measures, the three most commonly used anthropometric indices are weight-for-height, height-for-age, and weight-for-age; According to WHO criteria, (WHO technical report, 1995) SD-scores<-2 for weight-for-height and height-for-age describe acute and chronic malnutrition respectively. BMI as a new indicator has been developed by WHO for the first time to assess (the thinness of a child and hence its probability to indicate malnutrition of children) the weight of children (De Onis M et al, 2006). Weight-for-height index has been suggested as valid criteria for the identification and treatment progress of severe acute malnutrition in children (Isanaka S et al, 2009). These indexes can be used for screening of chronic and acute malnutrition but their diagnostic value is limited when attempting to identify children at early stages of undernutrition or patients at risk of deterioration in nutritional status as the result of medical condition.

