There is no agreement concerning the most appropriate criteria to be used. What is needed is a valid and accessible tool to establish the early identification and desirable management of nutritional risk in children. . There remains a great variation in the criteria used to define malnutrition, with each method having its own limitations.

Pre-existing paediatric nutrition screening tools

Recently a variety of nutritional screening tools have been developed for assessment of nutritional status of children in hospital setting, including; SGNA (Subjective Global Nutritional Assessment) (Secker and Jeejeebhoy, 2007), STAMP (Screening Tool for the Assessment of Malnutrition in Paediatric) (McCarthy H, et al. 2008 and More J, 2008),

STRONG kids (Screening Tool Risk on Nutritional Status and Growth) (Jessi M. Hulst et al., 2010), and PYMS (Paediatric Yourhill Malnutrition Score). These all use the internationally recognized predictors of undernutrition: clinical assessment, dietary intake and anthropometric measurements. Each of these components bears a nutrition risk score, and overall score corresponds to the overall undernutrition risk of the patient. Although, recent studies have attempted to develop appropriate nutritional screening tools for children on admission, they are not useful for infants as they have not been validated except of STRONG kids (Screening Too Risk on Nutritional Status and Growth) which has been developed for hospitalized children as well as infants.

Development of the infant Paediatric Yorkhill Malnutrition Score (iPYMS)

A project team, consisting of senior nursing, dietetic, research academic and medical staff have developed a preliminary tool that would be both simple and quick to use. The infant nutritional screening tool will consist of four fields;

1. Weight centile (using admission weight)
2. Poor weight gain (by parental report)
3. Reduced intake
4. Effect on nutrition of current illness

On admission this tool would be completed by the nurse (researcher initially). A score of 0 or 1 classify patient at a low and median risk of undernutrition and a score of 2 or more reflects a high risk of undernutrition.

Purpose of the Study

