The purpose of this study is to evaluate a proposed malnutrition screening scheme for infants - the infant Paediatric Yorkhill Malnutrition Screening(iPYMS)score to discover how well it distinguishes infants who are well-nourished from those undernourished or at risk of undernutrition (discriminant validity).

We also need to compare it with results of other reputable nutritional measurements (concurrent validity).

Hypotheses

1. Most infants with low fat levels or at high risk of undernutrition with Paediatric Global Nutritional Assessment (PGNA) will be identified by a high infant Yorkhill Malnutrition Score (sensitivity).
2. Infants with high infant Yorkhill Malnutrition Score will have lower fat levels than infants with low score (discriminant validity).
3. There will be a moderate to good agreement and concordance between infants who have been screened with iPYMS and STRONG kids.
4. Explore the utility of bioelectrical impedance and an infant eating behaviour scale in detecting infants with malnutrition
5. Relate the malnutrition risk to length of hospital stay

Method

The researcher will pilot the study and this will be the opportunity receive feedback on the study design. The researcher will first complete the iPYMS scoring sheet for each

child and then the questionnaires (SGNA and Infant EBQ) will be completed by the main carer of patient.

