Participant of the study will be all patients newly admitted to selected wards (medical and general surgical wards) at the Royal Hospital for Sick Children (and possibly RAH Paisley). An average of 8 patients per day are admitted to the relevant wards and we will aim to recruit a total of 200 over a 4 month period, after an initial pilot with up to 20 patients. Children aged 1 -24 months are the subjects of this study because the purpose of this study is to develop a screening tool for infants.

Exclusions

- Patients in the short stay ward, intensive care or high dependency unit, Oncology unit, NICI and PICM, Cardiology (SA),
- Patient who have been transferred from neonatal units and PICM and NICM.

Sample Size- Power Calculation

Using the Altman monogram 45 subjects in each group (135 in total) would give 90% power to detect a difference of 0.66SD (1 centile space) in skinfolds between any two of the 3 groups. 70 subjects in each group (210) gives 80% power to detect a difference of 0.5SD in skinfolds between any two of the 3 groups.

It is likely that not all children will have complete measures so we will aim to recruit 200 subjects.

Sample Selection

Quota sampling will be used to obtain three equal groups of patients with different undernutrition scores (low, medium, high), until the desirable number of patients in each group is achieved. We will oversample high risk patients (expected to be only 10-20% of all patients) if necessary by screening all eligible patients using iPYMS and proceeding to full assessment for only those scoring high risk. In other word. a) The majority of patients screened at high risk of undernutrition. b) Every third child screened at medium risk of undernutrition. c) Every tenth child screened at low risk of undernutrition (Gerasimidis K et al, 2010).

We expect that malnutrition will be identified in between 10-30% of infant studied. If previously unrecognised this means they can then be referred for further assessment.

Recruitment

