The researcher will identify those patients eligible for screening by visiting the wards daily and obtaining details of new admissions from the nursing staff. She will then give an information leaflet to the patient's carer to read and answer any immediate questions. After at least one hour she will return to the ward and if the carer is happy to participate, the researcher will ask him/her to complete a consent form. A copy of the consent form will be given to the carers and another will be placed in the child's medical notes.

The material will be in written in a form suitable for anyone who can read English. We will not be able to include those infants where neither carer was able to read English.

Due to short admission periods usually most of the children will be discharged during the first day of stay. We aim to complete assessment on the next day after admission

Outcome Measurements

Parental questionnaires

1. Global Nutritional Assessment for infants (SGNA)

The researcher will ask the main carers of patients to complete the eating behavior questionnaire about the infant's diet (type of milk, supplementary feeding and weaning diet), weight loss (poor weight gain), gastrointestinal symptoms, and daily activity. A rough visual assessment of the child's muscle stores and fat will be carried out by the researcher. This is a global nutritional assessment procedure recently validated in paediatric patients as a measure of current and future nutrition risk (Secker & Jeejeebhoy, 2007). A copy of the assessment form and the article that describes this method is attached for the ethics committee attention.

2. Infant EBQ

This questionnaire has been developed using population data from a cohort study and is designed to identify infants at risk of weight faltering. This will be completed by the main carers of patients to assess the patient's general appetite and eating behaviour

Measurements

3. Triceps (TSF) and subscapular skinfold thickness

Measurement of the thickness of the skin of the arm (triceps) and shoulder blade (subscapular) will be done as a measure of fat store. Briefly the parent will take off their top clothing and the researcher will measure the skinfold thickness with Holtain calipers. This measurement will be to some extent inconvenient for patients particularly those who are <1 year of age.

4. Weight and length

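### The Recruitment section expects most infants to leave on the first day but aims to assess them on the next, so in-person measurements may come only or disproportionately from longer stayers

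*Protocol*

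**What the plan says.** In two adjacent statements, the Recruitment section of the protocol says that "most of the children will be discharged during the first day of stay. We aim to complete assessment on the next day after admission". It also has the researcher visit the wards daily, hand over a leaflet, and return at least an hour later for consent.

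Other sections set the population and the purpose:

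- Subjects: "Participant of the study will be all patients newly admitted to selected wards".
- Exclusions: the list begins with "Patients in the short stay ward".
- Sample Selection: "Quota sampling will be used to obtain three equal groups of patients with different undernutrition scores".
- Method: "The researcher will first complete the iPYMS scoring sheet for each" child, with the carer questionnaires after that. No interval is given.
- Development of the iPYMS: the tool is meant for use on admission, and its first field uses the admission weight.
- Introduction: "malnutrition has been associated with an increase in length of hospital stay". Relating malnutrition risk to length of stay is listed under Hypotheses, and length of stay is named a secondary outcome under Outcome Measurements.
- Analysis-Statistics: false negatives and false positives are defined against body composition and/or the SGNA.

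**The concern.** On a plain reading, the assessment is timed for a point at which most of the children have gone home. The measurements that make up the reference standard cannot be taken from records or by questionnaire. Entry to the reference sample would then depend on length of stay, which is a study outcome and, by the protocol's own account, is related to malnutrition.

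Quota sampling does not remove this. It fixes how many infants are assessed at each iPYMS level. Within a level, the infants still on the ward may differ nutritionally from those who have left. The false-negative and false-positive proportions, and the comparison of skinfolds between iPYMS groups on which the sample size rests, would then describe longer stayers rather than the admissions the tool is meant to screen.

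**Working it through.** No stated figure underlies this point, so there is none to reproduce. The check is a comparison of passages, followed by two small calculations on assumed inputs.

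**1. What needs the infant and researcher together.** Under Outcome Measurements: skinfolds by caliper, re-weighing and length, mid upper arm circumference by tape, impedance by electrodes, and the visual rating of fat and muscle for the SGNA and STRONGkids. Parental reports, admission weight and length of stay do not need it.

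**2. What the protocol provides for early leavers.** It gives no same-day rule, no post-discharge visit, and no rule for a screened infant who leaves before assessment. The sample size section expects some incomplete measures and sets the target at 200. That protects numbers but not representativeness. The one-hour wait comes before consent. No wait is imposed between consent and measurement, so same-day measurement is possible but is not stated.

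**3. Who would be measured.** Let L be the share staying beyond the first day (below 0.5, since most leave). Let f be the chance that a first-day discharge is still measured, relative to a longer stayer. The protocol gives neither value. The share of longer stayers among measured infants is L / (L + f(1 − L)); for example, 0.40 / (0.40 + 0.25 × 0.60) = 73%.

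| L (assumed) | f = 0 | f = 0.10 | f = 0.25 | f = 0.50 |
|---|---|---|---|---|
| 0.40 | 100% | 87% | 73% | 57% |
| 0.30 | 100% | 81% | 63% | 46% |
| 0.20 | 100% | 71% | 50% | 33% |

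The literal plan is f = 0. For any f below 1 the share exceeds L, so longer stayers are over-represented. They are not a majority in every cell.

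**4. Whether a direction follows (hypothetical).** Assume 10% undernourished, sensitivity 70% and specificity 90%. The share scoring high is 0.10 × 0.70 + 0.90 × 0.10 = 0.16, inside the protocol's 10-20%. The undernourished share is 0.07 / 0.16 = 0.4375 among high scorers and 0.03 / 0.84 = 0.0357 among the rest. If undernourished infants are r times as likely to be measured, a share p becomes pr / (pr + 1 − p). At r = 1.5 the shares become 0.538 and 0.053.

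- *Three equal groups, cross-tabulated without weights*, with the same share assumed in the low and medium groups. Apparent sensitivity is p(high) / [p(high) + 2p(other)]. It is 0.4375 / (0.4375 + 0.0714) = 86% at r = 1. It is 0.538 / (0.538 + 0.105) = 84% if r = 1.5 in every level, and 0.538 / (0.538 + 0.071) = 88% if r = 1.5 among high scorers only.
- *Reweighted to screened numbers*, an analysis the protocol does not state. The corresponding values are 70%, 66% and 74%.

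Under either analysis, the sign depends on an input the protocol does not give, and at r = 1 there is no selection effect. The gap between 86% and 70% comes from the quota sampling and is a separate matter.

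**5. Skinfold comparison.** If the measured infants are leaner than their level as a whole by the same amount in each group, the group differences do not change. If the amount differs between groups, the differences may shrink or widen. The protocol does not say which applies.

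**The case against.** The strongest reply is that the two sentences can be read together. The first speaks of short admissions, and the second can be taken as the response: finish promptly, no later than the next day. If the first day means 24 hours and the next day means the next calendar day, an infant admitted in the evening and discharged the following afternoon satisfies both. The timing is only an aim. The short stay ward is excluded, so the loss on the study wards is smaller if the discharge statement counts those children. A pilot of up to 20 patients is planned and could expose a timing problem.

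All of this stands as mitigation. None of it is written as a rule, however, and the discharge statement sits in the section describing the children to be recruited. Nor can the matter be left to an analysis plan: when the reference is measured is trial conduct, and no analysis recovers measurements that were not taken.

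A reader might infer that sensitivity will be understated by several points. The documents do not support that: prevalence, accuracy and the retention ratio are all assumed, and the direction reverses under a different assumption. A reader might also infer that the measured sample must consist mainly of longer stayers. That holds on the literal plan, but not if a fair share of early leavers is measured, as the table shows. Missing infants who come and go between daily ward visits is an ordinary limit of ward recruitment and contradicts nothing in the protocol.

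**Conclusion.** The two sentences conflict as written, and the protocol does not resolve the conflict. Followed literally, every in-person measurement comes from infants who stay past the first day, a minority of admissions by the protocol's own expectation. With partial capture of early leavers, longer stayers are still over-represented. This matters because the selection runs through a study outcome that the protocol ties to malnutrition.

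The conclusion goes no further than that. It rests on the plain meaning of the discharge and timing statements and on the absence of any other provision. The size and direction of bias in the error proportions and in the skinfold comparison cannot be derived. A reader might also expect the high-risk quota to fail. The protocol's figures do not settle that: 8 admissions a day over an assumed 120 days is 960. If 51% leave on day one, about 470 remain, of whom 47-94 are high risk at 10-20%. If 70% leave, 288 remain, of whom 29-58 are high risk. Against about 67 needed (200 / 3), the outcome depends on an unstated share.

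**What to change.** Reconcile the two sentences in the Recruitment section. State that iPYMS and, for infants selected for full assessment, the research measurements are done at the visit at which consent is signed (at least one hour after the leaflet), with the next day only as a fallback when that visit cannot be completed.

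As a minor addition, report by iPYMS level the number of consented, screened infants selected for full assessment who left before it, with their length of stay. This shows how much selection remains; the point does not depend on it.

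The cost is protocol wording and one short table. The researcher and the visit are already planned, and length of stay is already collected. The downside is a longer first visit, and selection is reduced rather than removed.

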Weight will have been measured on admission. The researcher will re weight and measure length using the ward scales and recumbents stadiometer or our own portable equipment.

5. Mid upper arm circumference (MUAC)

The researcher will measure the circumference of their mid upper arm using a simple measuring tape.

6. Bioelectrical impedance (BIA)

This has been developed for assessment of nutritional status in children based on indices of lean and fat adjusted for body size (Wright CM et al, 2008). We want to discover whether this method is practical and effective in this young age range and how it relates to nutrition score. Self adhesive electrodes are attached to the right wrist and ankle while the child lies on the bed. Three reading are taken, while, the electrodes are attached

The infants may become briefly upset by being measured. If they become very upset and uncooperative that measurement will be abandoned.

Additional elements

7. STRONG kids (Screening Tool Risk on Nutritional Status and Growth)

The researcher will extract equivalent items for SGNA about the child's food intake, diarrhoea, vomiting, weight loss or poor weight gain or no weight gain, during the few days before admission. An observational assessment of patients will be also carried out by researcher in terms of diminished subcutaneous fat, muscle mass and hollow face (subjective clinical assessment- the same as b). In addition, the researcher will use information recorded in the medical notes of the patient to assess patients' underlying illness with a risk of malnutrition (Anorexia nervosa, Celiac disease, Cystic fibrosis, cardiac disease, and trauma).

8. Length of hospital stay (LOS)

Length of hospital stay as a secondary outcome will also be collected from hospital admissions statistics or through the notes.

9. Growth trajectory

Patients' birth weight will be collected by the maternal report in order to calculate weight trajectory.

Analysis-Statistics

Data will be entered into the electronic database of SPSS v15. The paper data will have names and dates of birth recorded in order to allow linkage to hospital discharge data. The electronic data will have only enough personal information to link it uniquely with the paper record. The anonymised electronic data will be stored on the password protected university network.

The raw measurements of body composition, height, weight. Skinfolds and mid upper arm circumference will be converted into standard deviation scores.

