- Height and weight will be converted into standard deviation scores according to the UK 1990 reference data.
- Skinfolds and mid upper arm circumference will be converted into standard deviation scores according to the World Health Organization reference values. A value less than -2 standard deviation scores denotes a patient at high risk of undernutrition.

Patient iPYMS outcome (nutrition risk), will be cross-tabulated with the respective nutrition risk from the Paediatric Subjective Global Nutrition Assessment or, body composition assessment. The proportion of patients at risk of undernutrition (according to body composition assessment and/or the Paediatric Subjective Global Nutrition Assessment) who were not identified by the iPYMS will be recorded as false negatives. On the contrary, the proportion of patients at low risk of undernutrition (according to body composition assessment and/or the Paediatric Subjective Global Nutrition Assessment) who were screened as at high risk of undernutrition by the iPYMS will be recorded as false positives.

The mean values per group compared using t-test and anova and the categorical data compared using chi squared and logistic regression analysis.

We will use this data to test the utility of PYMS score, growth trajectory, body mass index and behaviour questionnaire as predictors of low adiposity and stunting
K-statistics will be used for Agreement of the methods.

References

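### The STRONGkids weight item is given a look-back of only a few days, which suits intake and gut symptoms but not growth in infants aged 1-24 months

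*Protocol*

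**What the plan says.** Additional elements, item 7, is the protocol's only instruction for scoring these STRONGkids items. It opens with "The researcher will extract equivalent items for SGNA about the child's food intake", adds diarrhoea and vomiting, and closes the list with "weight loss or poor weight gain or no weight gain, during the few days before admission". As punctuated, the window applies to every item in the list, weight included.

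The two related weight items carry no window. The iPYMS field is "Poor weight gain (by parental report)". The SGNA questionnaire asks the carer about "weight loss (poor weight gain), gastrointestinal symptoms, and daily activity", among other things.

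The STRONGkids score is used for hypothesis 3: "There will be a moderate to good agreement and concordance between infants who have been screened with iPYMS and STRONG kids". The Method section makes this comparison the test of concurrent validity. Analysis-Statistics adds "K-statistics will be used for Agreement of the methods".

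The population is stated under Subjects: "Children aged 1 -24 months are the subjects of this study". They are new admissions to medical and general surgical wards.

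**The concern.** Intake, diarrhoea and vomiting change within days, so a few-days look-back suits them. Poor or absent weight gain describes growth, and at this age growth needs a longer span to show. If the sentence is followed literally, two errors are likely:

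- An infant whose weight has been flat for two months, but who has not changed this week, need not be picked up by a question about the last few days.
- A well-grown infant with two days of gastroenteritis may be recorded as losing or not gaining weight because of fluid loss, on top of being recorded for diarrhoea and vomiting.

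In both cases the item follows the acute illness and not nutritional status. Concurrent validity rests on comparing iPYMS with this STRONGkids score, so a badly windowed item makes the kappa harder to interpret. An answer taken over the wrong window also cannot be re-scored afterwards.

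**Working it through.** The protocol states no figure that depends on this window, so there is nothing to reproduce. Two checks are possible.

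**1. The text, section by section.**

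| Item | Source | Look-back stated |
|---|---|---|
| STRONGkids intake, diarrhoea, vomiting | Additional elements, item 7 | a few days |
| STRONGkids weight loss, poor gain or no gain | same sentence | a few days |
| SGNA weight question | Parental questionnaires, item 1 | none |
| iPYMS poor weight gain | Development of the iPYMS, field 2 | none |

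Could another section rescue the weight item? The Measurements section uses the admission weight and a re-weigh by the researcher. Item 9 says "Patients' birth weight will be collected by the maternal report in order to calculate weight trajectory", but does not link this to STRONGkids. The Method section mentions earlier weights without dating them or linking them to STRONGkids. So nothing supplies a longer look-back for the item.

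**2. Can growth be seen over a few days?** The inputs are assumptions, not taken from the documents: normal gain g = 8, 15 or 30 g/day, and SD of a single weight s = 50, 100 or 150 g (feeds, voiding, scales). For a window of d days:

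- gain/noise ratio: R = g·d / (√2·s)
- chance of misclassifying a zero-gain or a normally growing infant, with the cut midway between them: 1 − Φ(R/2)

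Worked examples:

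- g = 8, d = 3, s = 150: R = 24/212.1 = 0.11; misclassification 48%.
- g = 30, d = 3, s = 50: R = 90/70.7 = 1.27; misclassification 26%.
- g = 30, d = 5, s = 50: R = 150/70.7 = 2.12; misclassification 14%.
- g = 8, d = 60, s = 150: R = 480/212.1 = 2.26; misclassification 13%.

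| Window | R, range | Misclassification, range |
|---|---|---|
| 3-5 days | 0.11-2.12 | 14-48% |
| 28 days | 1.06-11.9 | 0-30% |
| 60 days | 2.3-25 | 0-13% |

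Of the 18 combinations at 3 or 5 days, 14 have R below 1. The four exceptions are g = 30 with s = 50 at 3 days (1.27) and at 5 days (2.12), g = 30 with s = 100 at 5 days (1.06), and g = 15 with s = 50 at 5 days (1.06). Growth over a few days is therefore usually, but not always, hidden in ordinary variation.

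This calculation supposes two weighings. The protocol does not plan them for this item, so the percentages show what the window could reveal at best. They are not error rates of the item as collected.

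**The case against.** The strongest reply has four parts.

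*The item is carer-reported.* Paired-weighing arithmetic does not describe how a carer answers. That stands: the percentages are not the item's error rates, and a carer may well mention two months of flat weight whatever window is asked about. But a carer with no recent weight is unlikely to judge a few days' growth better than two weighings would, so the window is not rescued.

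*It may be loose wording.* The closing phrase may have been meant only for intake and gut symptoms, and the sentence paraphrases a published instrument whose form is not shown. This is possible. As written it still instructs the researcher to use the short window for weight, and the same edit cures it.

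*The tools may not differ.* A reader might infer that iPYMS, SGNA and STRONGkids score weight on different time bases. The documents do not show this: the iPYMS and SGNA items state no window, and the iPYMS sheet and SGNA form are not shown. Silence is not a different window.

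*Kappa need not fall.* A reader might infer that the window lowers agreement by a calculable amount. It does not follow. STRONGkids item weights and class limits are not in the protocol, and iPYMS also scores reduced intake and the effect of current illness, so one acute episode can raise both tools together. A simulation shows how open the direction is. Take bivariate normal latent scores with correlation 0.95 and iPYMS cut into thirds, and raise 30% of the STRONGkids ratings below the top class by one class. Unweighted kappa falls from 0.72 to 0.53 if STRONGkids is also cut into thirds, but rises from 0.28 to 0.30 if STRONGkids splits 60/30/10. The correlation, the splits and the 30% are all assumed.

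**Conclusion.** The point holds as a fault in a stated rule. The protocol applies a few-days look-back to weight loss, poor gain and no gain, and nothing elsewhere corrects it. In acutely admitted infants such an item would tend to capture the current illness and miss sustained faltering. That weakens the test of hypothesis 3.

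Two stronger readings go too far. Growth over a few days is not invisible: on the assumed ranges, fast growers weighed precisely are an exception. And no figure can be put on the change in kappa, nor a sign.

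The fault concerns one item of one comparator, serving one of five hypotheses. It does not touch the skinfold comparisons on which the sample size is based. It is still worth correcting, because the correction is nearly free beforehand and the answers cannot be re-scored later.

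**What to change.** Before data collection:

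1. In Additional elements, item 7, apply the few-days window to food intake, diarrhoea and vomiting only.
2. Give the weight item (loss, poor gain or no gain) its own look-back of weeks to months. Check it against the STRONGkids form so that the comparator is used as its form defines it.
3. State the look-back of the iPYMS poor-weight-gain field and of the SGNA weight question, so that the tools can be compared.
4. Score each tool's weight item from its own question. Copying one carer answer into both iPYMS and STRONGkids would make the tools share an item and could inflate the agreement under test.

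The cost is one or two sentences in the protocol and on the scoring sheet. No extra measurement, staff or patients are needed.
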